9.9.2 Vital Signs and Weight

Respiration rate (breaths/minute), temperature (°C), and weight (kg) will be obtained at each clinic visit. Supine and standing systolic and diastolic blood pressure (mmHg) and supine and standing heart rate (beats/minute) will be collected at the Baseline, Week 8, and End-of-Treatment/Early Termination visits. Seated blood pressure and heart rate will be collected at all other visits.

Weight, respiration rate, temperature, seated/supine systolic and diastolic blood pressure, and seated/supine heart rate, and the corresponding change from baseline, will each be summarized by visit using descriptive statistics.

A listing of weight and vital sign assessments will also be provided.

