Rollover subjects will have an additional telephone contact at Week 5 with the same activities.

Switch subjects will have additional telephone contacts one week prior to their Baseline visit and at Week 7 to remind them to complete the diary card and to take or hold the morning dose on the day of their Baseline and Week 8 visits as per their assigned cohort (Rich or Sparse) dosing requirements. In addition, subjects will be reminded to return diary cards at the Baseline and Week 8 visits.

6.3.2 Clinic Visits (Weeks 4, 8, 15, 28 and every 13 weeks thereafter [all ± 3 days])

See the Schedule of Events A and B for a detailed summary of activities.

Long term treatment period clinic visits includes the following activities:

- Assessment of adverse events, chorea control (in consultation with the subject and caregiver) and concomitant medication use
- Brief physical examination (Week 28)
- Weight
- Vital signs (at Week 8, include orthostatic blood pressure and pulse)
- At Week 4, provide **Switch** subjects with a diary card to record the start time of their last meal and the time of their last dose prior to the Week 8 visit and ask them to bring the diary with them to the next clinic visit.
- Collect and review diary card (Week 8 **Switch** subjects only)
- For subjects on allowed doses of citalopram (Celexa) or escitalopram (Lexapro, Cipralext): Perform a 12-lead ECG if the dose of study drug has been increased since the last ECG was collected (Week 4)
- 12-lead ECG (Week 8)
- Clinical laboratory tests: serum chemistry, hematology, and urinalysis (Weeks 8 and 28, and every 26 weeks after Week 28)
- Urine pregnancy test (women of child-bearing potential only)(Week 28 and every 26 weeks thereafter)

- Blood sampling for PK (Week 8, **Switch** subjects only) for SD-809 ER
- Administer SD-809 post PK sample (Switch subjects scheduled for morning visits only)
- Hospital Anxiety and Depression Scale (HADS)
- Columbia Suicide Severity Rating Scale (C-SSRS): Since Last Visit version
- Montreal Cognitive Assessment (MoCA[®])
- Unified Huntington's Disease Rating Scale (UHDRS)
 - Motor
 - Cognitive
 - Behavior
 - Functional assessment (Week 28)
 - Independence (Week 28)
 - TFC (Week 28 and every 52 weeks thereafter)
 - Summary (Week 28)
- Unified Parkinson's Disease Rating Scale (UPDRS): dysarthria item
- Barnes Akathisia Rating Scale (BARS)
- Epworth Sleepiness Scale (ESS)
- Swallowing Disturbance Questionnaire (SDQ)

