7.2 Safety Endpoints

Safety and tolerability will be assessed throughout the study by monitoring the following:

- Incidence of adverse events (AEs), serious AEs (SAEs), severe AEs, drug-related AEs, and AEs leading to withdrawal during the following periods:
 - The entire post-baseline period
 - During the Titration Period (from Day 1 to the end of Week 8) in Rollover subjects
 - During the Dose-Adjustment Period (from Day 1 to the end of Week 4) in Switch subjects
 - During the Extended Dose-Adjustment Period (from Day 1 to the end of Week 8) in Switch subjects who undergo dose adjustment between Weeks 4 and 8 (if at least 10% of Switch subjects have had a dose adjustment between Week 4 and Week 8)
 - During the Stable-Dose Period (Week 8 to end of study)
- Observed values and changes from baseline in clinical laboratory parameters (hematology, chemistry, and urinalysis)
- Observed values and changes from baseline in vital signs
- Observed values in ECG parameters and abnormal findings

- Numbers of subjects with QTcF values > 450 msec, > 480 msec, > 500 msec
- Counts and percentages for Columbia Suicide Severity Rating Scale (C-SSRS)
- Observed values and changes from baseline in the following:
 - Unified Huntington Disease Rating Scale (UHDRS)
 - Unified Parkinson's Disease Rating Scale (UPDRS) (dysarthria)
 - Barnes Akathisia Rating Scale (BARS)
 - Hospital Anxiety and Depression Scale (HADS)
 - Epworth Sleepiness Scale (ESS)
 - Montreal Cognitive Assessment (MoCA[®])
 - Swallowing Disturbance Questionnaire (SDQ)
- Duration of time to achieve a stable dose of SD-809, defined as the number of days from Day 1 until the first day at which the subject was taking the dose level they were receiving at Week 8.

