8.7 Comments on Statistical Analysis

The following general comments apply to all statistical analyses and data presentations:

- Unless otherwise specified, all data will be summarized separately for the Rollover Cohort and the Switch Cohort.
- Summaries will include frequencies and percentages for categorical data and the number of observations, mean, standard deviation, median, minimum, and maximum for continuous data.
- Duration variables will be calculated using the general formula: (end date – start date) + 1.
- Unless specified otherwise, for subjects in the Switch cohort, the baseline value is the last available value prior to the first administration of SD-809 on Day 1. For Rollover subjects from the First-HD study, for assessments that were scheduled to be performed at Week 13 of that study or the Baseline visit of the ARC-HD study, the baseline value is the last available off-treatment (at least 4 days after the last administration of study drug) value prior to administration of SD-809 on Day 1. For assessments that were not scheduled to be performed at Week 13 of the First-HD study or at the Baseline visit of the ARC-HD study, the baseline value is the last available value prior to administration of study drug on Day 1 of the First-HD study. For the Switch cohort, the baseline value used for calculating change from baseline for TMC and the total motor score will be the mean of the values from the Screening and Baseline visits.
- If the reported value of a clinical laboratory parameter cannot be used in a statistical summary table (e.g., a character string is reported for a parameter of the numeric type), a coded value must be appropriately determined and used in the statistical analyses. In general, a value or lower or upper limit of normal range such as '<10' or '<5' will be treated as '10' or '5', respectively, and a value such as '>100' will be treated as '100.' However, the actual values as reported in the database will be presented in data listings.
- Individual subject listings of all data represented on the eCRFs will be provided to facilitate the investigation of tabulated values and to allow for the clinical review of all data.
- Version 9.4 of SAS statistical software package will be used to provide all summaries, listings, and graphs described in this document.

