8.9 Analysis Visit Windows

For efficacy and safety by-visit analyses, data collected at post baseline scheduled visits will be included using their nominal visit. Data collected at early termination, end of treatment, and unscheduled visits will be assigned to a visit window as described below. All scheduled visits will be assigned a target study day; for the determination of target days, weeks will be assumed to have 7 days. Thus, Week 4 would have a target day of $4 \times 7 = 28$ days. For each visit, a visit window will be assigned so that anything from the midpoint to the prior target day to the midpoint to the following target day will be assigned to that visit window as shown in Table 3 below. The following rules concerning visit windows and selecting records for analysis will be used:

1. Scheduled visit has precedence.

2. If there are multiple records of the same scheduled visit, the record closest to the target day will be used for analysis. If two records are equidistant, then the earlier one will be used.
3. For a given visit, if there is no data from a scheduled visit, data from an unscheduled visit that occurs in the visit window will be used for analysis.

Table 3: Analysis Visit Window

| Visit | Target Day | Visit Window |
|-----------------------------|------------|--------------|
| Screening | -5 | (--, -5) |
| Screening Telephone Contact | -2 | (-4, -2) |
| Baseline | -1 | (-1, -1) |
| Week 1 | 7 | (1,10) |
| Week 2 | 14 | (11-17) |
| Week 3 | 21 | (18, 24) |
| Week 4 | 28 | (25, 31) |
| Week 5 | 35 | (32, 38) |
| Week 7 | 49 | (39, 52) |
| Week 8 | 56 | (53, 80) |
| Week 15 | 105 | (81, 150) |
| Week 28 | 196 | (151, 241) |
| Week 41 | 287 | (242, 332) |
| Week 54 | 378 | (333, 423) |
| Week 67 | 469 | (424, 514) |
| Week 80 | 560 | (515, 605) |
| Week 93 | 651 | (606, 697) |
| Week 106 | 742 | (698, 787) |
| Week 119 | 833 | (788, 879) |
| Week 132 | 924 | (880, 970) |
| Week 145 | 1015 | (971, 1060) |
| Week 158 | 1106 | (1061, 1152) |
| Week 171 | 1197 | (1153, --) |

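### SAP 9.9.3 leaves the End of Treatment/ET orthostatic readings out of the summary, and SAP 9.9.2 does not say which posture supplies the baseline for seated/supine change

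*SAP*

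**What the plan says.** **Collection.** SAP 9.9.2 states that supine and standing blood pressure and heart rate "will be collected at the Baseline, Week 8, and End-of-Treatment/Early Termination visits", and that "Seated blood pressure and heart rate will be collected at all other visits". Footnote 2 of the SAP schedules agrees: Table 1 (Switch) attaches the orthostatic measurement to Baseline, Week 8 and End of Treatment, and Table 2 (Rollover) to Week 8 and End of Treatment. Protocol 6.6.5 lists Baseline, Week 8 and End of Treatment/ET. Protocol 6.3.3 repeats the requirement for the End of Treatment/ET visit.

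**Orthostatic summary.** SAP 9.9.3 names only Baseline and Week 8, both as the visits at which the readings are taken and as the visits to be summarised.

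**Change from baseline.** SAP 9.9.2 plans that "seated/supine systolic and diastolic blood pressure, and seated/supine heart rate, and the corresponding change from baseline, will each be summarized by visit". SAP 7.2 lists as a safety endpoint "Observed values and changes from baseline in vital signs". For Switch subjects SAP 8.7 says "the baseline value is the last available value prior to the first administration of SD-809 on Day 1". For Rollover subjects it takes the last off-treatment value. Neither rule mentions posture.

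**Windowing.** SAP 8.9 says "Data collected at early termination, end of treatment, and unscheduled visits will be assigned to a visit window". Table 3 has no End of Treatment row.

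**The concern.** The two adjacent SAP sections disagree about when orthostatic data exist. A programmer who follows 9.9.3 will produce supine-standing differences for Baseline and Week 8 and stop there. The one orthostatic measurement scheduled after Week 8, taken when exposure is longest, would not be tabulated.

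The second issue is what the seated/supine label means. Section 9.9.2 allots one resting posture to each visit, so the slash can be read as a single resting measurement whose posture alternates. A seated value at Week 28 would then be compared with a supine value from the Baseline visit. In a single-arm study no control group shows whether a step between visits comes from posture or from drug. What is at stake is the interpretation of a listed safety endpoint. SAP 8.1 plans no formal testing, so no error rate is involved.

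**Working it through.** There is no plan figure to reproduce. The check compares passages and counts visit rows.

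**Part (a): orthostatic time points**

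| Source | Baseline | Week 8 | End of Treatment/ET |
|---|---|---|---|
| SAP 9.9.2 | yes | yes | yes |
| SAP Table 1, footnote 2 (Switch) | yes | yes | yes |
| SAP Table 2, footnote 2 (Rollover) | not marked; cell imports C-15 Week 13 data | yes | yes |
| Protocol 6.6.5 | yes | yes | yes |
| Protocol 6.3.3 | – | – | yes |
| SAP 9.9.3 (summary) | yes | yes | no |

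Post-baseline time points collected: 2. Summarised in 9.9.3: 1. Not summarised: 2 − 1 = 1.

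There is one narrow route in. Under SAP 8.9 an ET reading on Days 53–80 falls in the Week 8 window and could stand in for a missing scheduled Week 8 record. That does not cover End of Treatment generally.

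**Part (b): posture of the change from baseline**

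Post-baseline clinic rows in SAP Table 3:

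- Switch: Weeks 1, 4, 8 and 15 (4 rows), plus Weeks 28 to 171 in steps of 13: (171 − 28)/13 + 1 = 12. Total 4 + 12 = 16.
- Rollover: Weeks 2, 4, 8 and 15 (4 rows), plus the same 12. Total 16.
- Only Week 8 is a supine visit among these, so 16 − 1 = 15 rows are seated under SAP 9.9.2.

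| Reading of seated/supine | Switch baseline under SAP 8.7 | Rows with seated minus supine |
|---|---|---|
| One parameter, no seated Baseline value used | supine, Baseline visit | 15 of 16 |
| Two parameters | seated for seated rows, supine for supine rows | 0 of 16 |

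On the second reading a seated Switch baseline is available. Screening carries no orthostatic footnote in Schedule A. A seated value may also exist at the Baseline visit, because Protocol 6.6.4 describes vital signs as taken sitting and excepts no visit. Protocol 6.3.2 treats orthostatic readings as part of vital signs: "Vital signs (at Week 8, include orthostatic blood pressure and pulse".

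**Rollover.** The baseline vital signs are imported from C-15 Week 13. Schedule B puts no orthostatic footnote on that cell, while Protocol 6.6.5 and SAP 9.9.2 list Baseline without a cohort exception. On the one-parameter reading, 15 of 16 rows are cross-posture if the imported value was supine. If it was seated, only Week 8 is (1 of 16). On the two-parameter reading no cross-posture change need arise.

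**Windowing.** Rule 1 of SAP 8.9 is "Scheduled visit has precedence". A supine End of Treatment/ET value therefore gives way where a scheduled record already fills the window. Where none does, it can enter that row. For example, after an attended Week 106 visit, a final reading on Days 788–879 falls in the Week 119 window. On the one-parameter reading, a supine value then sits in a row that otherwise holds seated values.

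**The case against.** The strongest reply is that part (b) shows no error. Section 9.9.2 says the measures and their corresponding changes are each summarised, which is compatible with like-for-like comparison. Held as separate parameters, they need no cross-posture change. The SAP was prepared with the 2017 case report forms in hand, and these would show which posture fields exist; they are not available here. This stands: the 15-of-16 count depends on one reading and cannot be presented as what the tables will contain.

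Several stronger inferences should also be resisted.

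- *That later orthostatic data go unreported except in listings.* This is too broad. The supine component at End of Treatment/ET is eligible for the 9.9.2 by-visit table through SAP 8.9. Only standing values and supine-standing differences lack a summary.
- *That most of the study has a mismatched baseline because Rollover subjects are the larger cohort.* The posture at C-15 Week 13 is not in these documents. A missing footnote on a cell that imports data is weak evidence either way.
- *That the omission in 9.9.3 is an undeclared departure from a protocol analysis.* Protocol 6.6.5 and 6.3.3 specify collection. Protocol 8.3 and 8.4 name no supine-standing analysis, and 8.3 leaves end-of-study vital-sign summaries to be given where appropriate.

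It is also fair to say that all values will be listed and that nothing is tested. That limits the consequence of both parts but resolves neither.

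**Conclusion.** Part (a) holds without any choice of reading. SAP 9.9.3 contradicts SAP 9.9.2, the SAP schedules and Protocol 6.6.5 and 6.3.3. Apart from the narrow Week 8 window route, Week 8 is the only post-baseline orthostatic summary in a study with visit windows to Week 171. Standing values and supine-standing differences at End of Treatment/ET are left to listings.

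Part (b) holds as a gap in specification. The Switch tables could have 15 of 16 or 0 of 16 cross-posture rows depending on how a programmer reads one phrase, and the SAP does not decide. The 15-of-16 count assumes one pooled parameter, the SAP 8.7 baseline taken from the supine Baseline visit, and no seated Baseline value used. It counts table rows, not subjects. The Rollover baseline posture cannot be confirmed from these documents.

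A reader might infer that the planned vital-sign changes are biased. The documents do not support that, because they neither establish the pooled reading nor give the size or direction of any posture effect.

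**What to change.** 1. **SAP 9.9.3.** Correct the statement of when orthostatic readings are taken. Add the supine-standing differences at End of Treatment/ET and their change from Baseline. Label End of Treatment and Early Termination separately, since an ET reading may come some time after the last dose.
2. **SAP 9.9.2.** Suggested wording: *Seated and supine blood pressure and heart rate will be summarised as separate parameters. Change will be calculated only from a baseline of the same posture; where none exists, observed values alone will be shown. Supine End of Treatment/ET values will not be placed in seated visit rows.*
3. **Reconcile** Protocol 6.6.4, Protocol 6.6.5, Schedule B and SAP 9.9.2 on which postures are recorded at Baseline, Week 8 and End of Treatment/ET. Confirm the posture of the imported C-15 Week 13 value.

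The cost is SAP wording, some table programming and one check of the C-15 records, with no new data collection. Rollover subjects may end up with observed-only tables for one posture.

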9.9.3 Orthostatic Vital Signs

Orthostatic blood pressure and heart rate will be recorded at Baseline and Week 8. The Baseline and Week 8 differences between supine and standing systolic and diastolic blood pressure and heart rate, and the change from Baseline to Week 8 in these differences will be summarized using descriptive statistics.

9.9.4 Physical and Neurological Examinations

Physical examination findings will be listed.

A complete neurological examination will include evaluation of the following categories:

- Cranial nerves
- Motor system (muscle strength, coordination)
- Sensory (sensation)
- Reflexes (muscle strength reflexes, plantar response)

Neurological examination findings will be listed.

9.9.5 Electrocardiogram (ECG)

A safety electrocardiogram (ECG) will be recorded at Screening and the Week 8 visit for all subjects. For subjects on allowed doses of citalopram or escitalopram, additional ECGs will be performed at Week 1 (Switch subjects) or Week 2 (Rollover subjects) and at Week 4 if the dose of study drug has been increased since the last ECG.

A cardiologist will provide a clinical interpretation of each ECG that will be recorded in the eCRF. ECG parameters that will be recorded include heart rate, PR interval, QRS duration, QT interval, and QTcF (QT interval corrected for heart rate using Fridericia's formula).

Descriptive statistics will be used to summarize ECG parameters at Screening and the Week 8 visit. Descriptive statistics will also be used to summarize QTcF values at Screening and the Week 8 visit for subjects with a QTcF value >450 msec at any visit. These analyses will be repeated for the Screening, Week 1 (Switch subjects) or Week 2 (Rollover subjects), Week 4, and Week 8 visits for subjects receiving allowed doses of citalopram or escitalopram at Baseline.

The number and percentage of subjects with normal, abnormal not clinically significant, abnormal clinically significant, and abnormal with clinical significance not specified ECGs will be summarized at Screening and the Week 8 visit. The number and percentage of subjects with PR >200 msec, QRS >100 msec, QT >500 msec, QTcF >450 msec, QTcF >480 msec, and QTcF >500 msec, will be similarly summarized. These analyses will be repeated for the Screening, Week 1 (Switch subjects) or Week 2 (Rollover subjects), Week 4, and Week 8 visits for subjects receiving allowed doses of citalopram or escitalopram at Baseline.

ECG results will also be listed.

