6.3 Long Term Treatment Period

All subjects will enter the long term treatment period after Week 2, although dose adjustment may continue in Switch subjects and titration may continue in Rollover subjects.

During long term treatment, all subjects will be contacted by telephone at Week 3 and will return to the clinic on Weeks 4, 8, 15, 28 and every 13 weeks thereafter for evaluation of safety and chorea control. In addition, Rollover subjects will have an additional telephone contact at Week 5. Switch subjects will have an additional telephone contact at Week 7, to remind subjects to complete diary card before the Week 8 visit. **Subjects who have not achieved a dose level that adequately controls chorea and is well tolerated by the Week 4 visit (Switch subjects) or Week 5 telecon (Rollover subjects) should have unscheduled visits or telephone contacts in order to further adjust their dose upward or downward.** Site interactions for dose adjustment should alternate between telephone contacts and clinic visits. During long-term treatment, further dose adjustments of SD-809 ER may be made, if necessary, but not more often than weekly and in increments of 6 mg (6 mg/day or 12 mg/day after a total daily dose of 48 mg is reached). Dose adjustments should be based on all available information including the subject's and caregiver's reports of adverse events and chorea control, information from rating scales and all safety evaluations. If subjects become non-ambulatory or require more aid than an assistive device during long term treatment, they will be permitted to remain in the study.

At the end of the long term treatment period, subjects will undergo a comprehensive evaluation, including physical and complete neurological exam, safety labs and 12-lead ECG and performance of all rating scales.

6.3.1 Telephone Contacts (One week prior to Baseline visit [Switch only]; Week 3 ± 3 days [All Subjects]; Week 5 ± 3 days [Rollover only]; Week 7±3 days [Switch only])

See the Schedule of Events A and B for a detailed summary of activities.

All subjects will be contacted by telephone during Week 3 to assess adverse events, chorea control (in consultation with the subject and caregiver), concomitant medication use, evaluation of study drug dose level and adjustment, if necessary and to schedule/confirm the next visit. Following the above assessments, study medication will be re-ordered according to specified procedures.

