6.3.3 Clinic Visit (End of Treatment \pm 3 days or Early Termination)

See the Schedule of Events A and B for a detailed summary of activities.

All subjects will stop study drug at the End of Treatment visit. Subjects will return to the clinic

for the following End of Treatment/ET end-of-long term treatment period assessments:

- Assessment of adverse events, chorea control (in consultation with the subject and caregiver) and concomitant medication use
- Physical examination, vital signs (including orthostatic blood pressure and pulse), and weight
- Complete neurological examination
- Clinical laboratory tests: serum chemistry, hematology, urinalysis, and urine pregnancy test (women of child-bearing potential only)
- 12-lead ECG
- Single PK Blood Sample (for Early Termination Visits, if within 48 hours of last dose, if possible)
- Hospital Anxiety and Depression Scale (HADS)
- Columbia Suicide Severity Rating Scale (C-SSRS): Since Last Visit version
- Montreal Cognitive Assessment (MoCA[®])
- Unified Huntington's Disease Rating Scale (UHDRS)
 - Motor
 - Cognitive
 - Behavior
 - Functional assessment
 - Independence
 - TFC
 - Summary
- Unified Parkinson's Disease Rating Scale (UPDRS): dysarthria item
- Barnes Akathisia Rating Scale (BARS)
- Epworth Sleepiness Scale (ESS)
- Swallowing Disturbance Questionnaire (SDQ)
- Assessment of medication accountability/compliance and collection of all study medication
- The next clinic visit will be scheduled/reconfirmed

Note: If the subject discontinues from the study early, every effort should be made to complete the early termination procedures as outlined above and in Schedule of Events A and B. In addition, subjects discontinuing prematurely from the study should have a follow up visit 1 week after discontinuing therapy and a follow up telephone contact 4 weeks after discontinuing therapy, if possible. The procedures outlined in Section 6.4 should be followed.

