- Number of subjects with on-treatment QTcF values > 450ms, > 480ms, > 500ms
- Observed values and changes in UHDRS, UPDRS (dysarthria), BARS, HADS, ESS, C-SSRS, and MoCA©
- Duration of time to achieve stable doing of SD-809 ER

8.5 *Sample Size*

Because this is an open label safety study, the sample size is not based on statistical considerations.

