| Medical History/Demographics | X | | | | | | | | | | | | | | | | |
| Vital Signs/Weight | X | | X ² | X | | | X | | X ² | X | X | X | X ² | X | | X | |
| Physical Examination | X ⁴ | | X | | | | | | | | X ⁴ | | X | | | | |
| Complete Neurological Exam | X | | | | | | | | | | | | X | | | | |
| Height | X | | | | | | | | | | | | | | | | |
| 12-lead ECG | X | | | X ¹⁶ | | | X ¹⁶ | | X | | | | X | | | | |
| Blood sampling for PK | | | X ¹² | | | | | | X ¹³ | | | | X ⁵ | | | X ⁵ | |
| Provide/Remind/Review diary Card for meal/dosing times | X ⁹ | X ⁹ | X ¹¹ | | | | X ¹⁰ | X ¹⁰ | X ¹¹ | | | | | | | | |
| Chemistry/Hematology/UA | X* | | X | | | | | | X | | X | X | X | | | | |
| CAG Repeat | X | | | | | | | | | | | | | | | | |
| Blinded CYP2D6 Genotype | X | | | | | | | | | | | | | | | | |
| Virology Screen (HBsAg) | X | | | | | | | | | | | | | | | | |
| Pregnancy Test/FSH ⁶ | S | | U | | | | | | | | U | U | U | | | | |
| HADS | | | X | X | | | X | | X | X | X | X | X | X | | | |
| C-SSRS ⁷ | X | | X | X | | | X | | X | X | X | X | X | X | | | |
| MoCA ⁸ | | | X | | | | X | | X | X | X | X | X | X | | | |
| UHDRS - Motor | X | | X | X | | | X | | X | X | X | X | X | X | | X | |
| UHDRS - Cognitive | | | X | | | | X | | X | X | X | X | X | X | | | |
| UHDRS - Behavior | | | X | X | | | X | | X | X | X | X | X | X | | | |
| UHDRS - Functional Assessment | | | X | | | | | | | | X | | X | | | | |
| UHDRS - Independence | | | X | | | | | | | | X | | X | | | | |
| UHDRS - TFC | X | | X | | | | | | | | X | X | X | | | | |
| UHDRS - Summary | | | X | | | | | | | | X | | X | | | | |
| UPDRS - Dysarthria | X | | X | X | | | X | | X | X | X | X | X | X | | | |
| SDQ | X | | X | X | | | X | | X | X | X | X | X | X | | | |

| Study Week → | Screening | | | Long Term Treatment | | | | | | | | | | Follow up | | Unscheduled | | |
|---|-----------|-----|-----------------------|---------------------|----|----|----|----|-----------------|----|----|------------------|-----------|------------------|---------|------------------|----------------|-----|
| | Up to -4 | -1 | Baseline ₁ | Dose Adjustment | | | | | | | | | | End of Treatment | 1 wk FU | 4 wk FU | | |
| Visit Window (days) → | | ± 3 | 0 | ± 1 | | | | | | | | | | | | | | n/a |
| Visit → | Screening | T1 | V1 | V2 | T2 | T3 | V3 | T4 | V4 | V5 | V6 | Vx ¹⁷ | End Tx/ET | FU | FFU | UV ¹⁸ | UT C | |
| Activity Visit type → | V | TC | V | V | TC | TC | V | TC | V | V | V | V | V | V | TC | V | TC | |

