- 18 For subjects requiring an Unscheduled Clinic Visit for any reason, assessments denoted with X should be performed; all other assessments are as indicated at Investigator's discretion (see Section 6.5 of the protocol).

Table 2: SCHEDULE OF EVENTS B – SUBJECTS *ROLLING OVER* FROM SD-809-C-15

| Study Week → | Screening | | Long Term Treatment | | | | | | | | | | Follow up | | Unscheduled | |
|--------------------------------------|-----------------------------|-----|---------------------|----|----------------|----|----------------|----|----|----------------|------------------|-----------|-----------|-----|------------------|----------------|
| | Baseline‡ | 1 | 2 | 3 | 4 | 5 | 8 | 15 | 28 | 28 + q13 wks | End of Treatment | 1 wk FU | 4 wk FU | | | |
| Visit Window (days) → | +3 | ± 1 | | | | | | | | | | | | | n/a | |
| Visit → | Prior Data from Study C-15† | V1 | T1 | V2 | T2 | V3 | T3 | V4 | V5 | V6 | Vx ⁹ | End Tx/ET | FU | FFU | UV ¹⁰ | UTC |
| Activity Visit type → | V | TC | V | TC | V | TC | V | V | V | V | V | V | V | TC | V | TC |
| Evaluate/Adjust Dose | | X | X | X | X | X | X | X | | | | | | | X | X ³ |
| Evaluate Capacity for consent | X§ [#] | | | | | | | | | | | | | | | |
| Informed Consent/Assent | X§ | | | | | | | | | | | | | | | |
| Research Advance Directive†† | X§ | | | | | | | | | | | | | | | |
| Screening/Demographics | X | | | | | | | | | | | | | | | |
| Selection Criteria | X | | | | | | | | | | | | | | | |
| Update Medical History | X | | | | | | | | | | | | | | | |
| Vital Signs/Weight | ** | | X | | X | | X ² | X | X | X | X ² | X | | X | | |
| Physical Examination | * | | | | | | | | | X ⁴ | X | | | | | |
| Complete Neurological Exam | * | | | | | | | | | | X | | | | | |
| Height | * | | | | | | | | | | | | | | | |
| 12-lead ECG | * | | X ⁸ | | X ⁸ | | X | | | | X | | | | | |
| Blood sampling for PK | | | | | | | | | | | X ⁷ | | | | X ⁷ | |
| Chemistry/Hematology/UA | * | | | | | | X | | X | X | X | | | | | |
| CAG Repeat ¹ | * | | | | | | | | | | | | | | | |
| Blinded CYP2D6 Genotype ¹ | * | | | | | | | | | | | | | | | |
| Pregnancy Test | U | | | | | | | | | U | U | U | | | | |
| HADS | ** | | X | | X | | X | X | X | X | X | X | X | | | |
| C-SSRS ⁵ | ** | | X | | X | | X | X | X | X | X | X | X | | | |
| MoCA ⁶ | X | | | | X | | X | X | X | X | X | X | X | | | |
| UHDRS - Motor | ** | | X | | X | | X | X | X | X | X | X | X | | X | |
| UHDRS – Cognitive | X | | | | X | | X | X | X | X | X | X | X | | | |

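### SAP 9.9.5 leaves the End of Treatment/Early Termination ECG out of every ECG table and plans no any-time on-treatment QTcF count, so the protocol's QTcF endpoint is tabulated only by visit up to Week 8

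*SAP*

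**What the plan says.** The protocol's endpoint (Section 8.4) is "Number of subjects with on-treatment QTcF values > 450ms, > 480ms, > 500ms". It names no visit. SAP 7.2 keeps the three thresholds, also without a visit limit, but drops the on-treatment qualifier.

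Protocol 6.3 calls for an evaluation at the end of long-term treatment "including physical and complete neurological exam, safety labs and 12-lead ECG", and 6.3.3 lists the ECG among the End of Treatment/ET procedures. The same section says "All subjects will stop study drug at the End of Treatment visit", so a planned End of Treatment ECG sits at the end of exposure. The ECG rows of SAP Tables 1 and 2 carry the End of Treatment/ET mark too.

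SAP 9.9.5 reads differently. On collection: "A safety electrocardiogram (ECG) will be recorded at Screening and the Week 8 visit for all subjects". On analysis: "Descriptive statistics will be used to summarize ECG parameters at Screening and the Week 8 visit". The normal/abnormal classification and the PR, QRS, QT and QTcF threshold counts follow at those same two visits. For subjects on citalopram or escitalopram at Baseline, the tables are repeated with Week 1 (Switch) or Week 2 (Rollover) and Week 4 added, again ending at Week 8. One further summary describes QTcF at Screening and Week 8 "for subjects with a QTcF value >450 msec at any visit". All ECG results are listed.

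**The concern.** This is a long-term safety study in which treatment runs until U.S. commercial availability. The only scheduled ECG that reflects long-term exposure has no place in the ECG tables. A subject is missing from the printed threshold counts if the only exceedance occurs at End of Treatment, at an ET ECG outside a tabulated window, or at an unscheduled ECG that is not tabulated (Protocol 6.5 allows these at the investigator's discretion).

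The denominator is affected as well. SAP 8.7 bases percentages on subjects with non-missing data, so a subject with no Week 8 record drops out of the Week 8 percentage. That figure then describes subjects with a Week 8 ECG and not all treated subjects.

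**Working it through.** The plan states no figure to reproduce, so the check sets the schedules against 9.9.5.

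**1. Scheduled ECGs against tabulated ECGs** (ECG rows of SAP Tables 1 and 2 and of the protocol's Schedules A and B)

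| ECG | Who | Tabulated in 9.9.5? |
|---|---|---|
| Screening (prior C-15 data for Rollover) | all | yes |
| Week 1 (Switch) or Week 2 (Rollover) | citalopram/escitalopram users | yes, subgroup |
| Week 4 | the same users, if dose increased since last ECG | yes, subgroup |
| Week 8 | all | yes |
| Weeks 15, 28, then every 13 weeks | none scheduled | – |
| End of Treatment/ET | all | no |

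In the text version, the SAP Table 2 row has lost one cell. The protocol's Schedule B is aligned and puts the last mark at End of Treatment/ET.

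Scheduled post-dose ECGs for a completer:
- not on citalopram/escitalopram: Week 8 + End of Treatment = 2, of which 1 is tabulated;
- on either drug at Baseline: 1 + (0 or 1) + 1 + 1 = 3 or 4, of which 2 or 3 are tabulated.

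In both cases the untabulated ECG is the only one scheduled after Week 8.

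**2. Do the SAP 8.9 windows supply the missing values?** End of Treatment, ET and unscheduled records are assigned to week windows and used only when the scheduled record is absent. Day 52 falls in Week 7 (39 to 52), which has no ECG table. Days 53 to 80 fall in Week 8. Day 81 falls in Week 15, which has no ECG table. For a subject not on citalopram/escitalopram, such an ECG therefore reaches a post-dose table only on days 53 to 80 and only if the scheduled Week 8 ECG is missing.

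**3. Does the >450 msec subset supply the count?** Its n does include a subject whose only exceedance is at End of Treatment. However, it shows values only at Screening and Week 8 and gives no count above 480 or 500. It also mixes in values from before the first dose in this study: exclusion 11 admits females up to 460 ms and right bundle branch block up to 480 ms. For Rollover subjects the Screening ECG comes from C-15, Week 12 or earlier.

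**4. Is it a declared change?** SAP 8.10 lists two departures from the protocol (the compliance range, and moving total maximal chorea and total motor score to efficacy). ECG is not among them. Elsewhere the SAP does not stop at Week 8: C-SSRS is counted at any time after baseline, laboratory results at each visit, and adverse events over the entire treatment period.

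**5. Size**
- Planned subjects: 80 + 36 = 116, with one End of Treatment/ET ECG each. At most about 116 records lack a column, less those windowed into a tabulated visit.
- Week 8 is day 56 and the last target day in SAP Table 3 is 1197: 56/1197 = 4.7%. The 1197 is the end of the window table, not a planned duration.
- Rollover subjects start at 6 mg/day and rise by at most 6 mg/day each week up to 48 mg/day. On the nominal schedule the highest dose being taken up to Week 8 is 6 + 7 × 6 = 48 mg/day, against a stated maximum of 72 mg/day. For that cohort the Week 8 column cannot describe ECGs at doses above 48 mg/day.

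**The case against.** The protocol does not use the words maximum or any time, and it leaves analysis detail to the SAP, so by-visit counts could be called a permissible implementation. SAP 7.2 keeps the endpoint without a visit limit, so 9.9.5 could be seen as incomplete and not as substituting something narrower. The consequences are also contained. Every ECG is read by a cardiologist and listed. Clinically significant abnormalities that lead to diagnosis or intervention are adverse events (Protocol 7.1.1), and these are tabulated over the whole treatment period. No formal testing is planned, so no inference depends on these tables.

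The points about consequence stand: they limit the safety risk and hold this below a critical fault. The point about wording stands only in part. A maximum-value table is one way to produce the endpoint, and others are possible. But a number of subjects with on-treatment exceedances most naturally covers every on-treatment ECG, and even a purely by-visit reading would need the End of Treatment visit. Listings and adverse event tables do not give a number of subjects above each threshold.

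**Conclusion.** The point holds. As written, 9.9.5 contradicts the SAP's own schedules on ECG collection and does not deliver the protocol's QTcF endpoint: its only scheduled long-term ECG goes untabulated, and no any-time on-treatment count is planned. It should be fixed, though no data are lost.

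The size can be stated only in records: 1 of 2 scheduled post-dose ECGs tabulated for most completers, and at most about 116 End of Treatment/ET records without a column. This is not a bound on missed exceedances. The documents give no QTcF exceedance or withdrawal rates, so no number of missed subjects follows. Nor are all of these ECGs necessarily on treatment: Protocol 6.8 limits the ET blood sample to visits within 48 hours of the last dose, and so foresees later ones. The conclusion assumes the current text of 9.9.5 governs the tables. The content of the interim analysis appendix is not shown and could not be checked.

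**What to change.** In SAP 9.9.5:

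1. Add End of Treatment/ET to the ECG collection sentence.
2. Add End of Treatment/ET under its own label as a summary visit for ECG parameters, classifications and thresholds. State in SAP 8.9 that ECGs are an exception to the reassignment of these records into week windows; otherwise they move to weeks with no ECG table.
3. Add the number and percentage of subjects, by cohort and overall, whose maximum on-treatment QTcF exceeds 450, 480 and 500 msec. Use every ECG after the first SD-809 dose in this study (scheduled, unscheduled, End of Treatment/ET), with subjects having at least one such ECG as the denominator.
4. Restore the on-treatment qualifier in SAP 7.2 and define it by a stated interval from the date of last dose, so that an ECG at the visit where drug is stopped counts and later off-drug ECGs are flagged separately. SAP 8.8 ends the treatment period at the last dose and does not settle this.

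If the Week 8 limit is intended, declare and justify it in SAP 8.10.

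The cost is SAP wording, one extra visit column and one new table, all from ECGs already collected, read and listed.
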